#### **9.9. Concomitant Medications**

With the exception of medications used for the symptomatic treatment of influenza-related symptoms, administration of any dose of a concomitant medication during the study period must be recorded by the study staff within the subject's study source documents (e.g., chart). This includes prescription medications as well as over-the-counter medications.

Medications, such as antipyretics and analgesics, used for the symptomatic treatment of influenza-related symptoms will be recorded separately. Subjects will record the type, date, and time of symptomatic medications in the subject diary supplied by BioCryst including the date and time of administration. Study staff will provide diary completion instructions to subjects during their first study visit.

Use of concomitant medications will be assessed and recorded at Screening, and daily throughout the duration of the study through the study completion visit at Day 14 or later.

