##### **10.1.2.2. Day 1/Post-dose**

The following procedures/evaluations will be performed post-dose on Day 1:

- Collect up to 3 plasma samples, where possible, during the following time periods, beginning from the end of dosing until release from the site. For each plasma sample the calendar date and 24-hour clock time of sample collection will be recorded:
  - One time point immediately following completion of the infusion
  - One time point from 30 minutes to 1 hour post-infusion
  - One time point from 1 hour to 3 hours post-infusion
- Train the subject/caregiver on the recording of the following in the subject diary:
  - Subject's body temperature, obtained at approximately 12-hour intervals each day until the temperature normalizes for 48 hours (and 4 hours from last antipyretic medication administration or immediately prior to administration).

- Instruct the subject to assess his/her time lost from work, if applicable, and the recording of the subject's ability to perform usual daily activities using a 0 to 10 visual analogue scale.
- Assessment of signs and symptoms of influenza twice daily beginning on Day 1 (see Section [10.2.2](#)).
- Review and record concomitant medications
- Obtain and record body temperature
- Review and record AEs

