3.3.8. Definitions and Terminology

Age

Age will be defined as the age in years at time of signing of informed consent for all subjects.

Confirmed Influenza

A subject will be confirmed as having acute influenza infection if any specimen for assay of influenza A or B antigen by RT-PCR obtained during the study is positive.

Baseline Value

For purposes of analysis, the baseline value is defined as the last value obtained prior to initiation of study drug (eg, the Baseline Pre-Dose value). Should this value be obtained after the injection of study drug, then the most recent value obtained prior to initiation of study drug will be used for the baseline value.

Day 1

Day 1 is the day/time that study drug is initiated.

Study Day

Study Day is defined relative to Baseline (Day 1). Thus, the study day of an event is calculated as:
Study Day = event date – date of Day 1 +1.

Days on Study

Days on Study is the number of days from Day 1 to the date of study completion or early termination as recorded on the Day 14/End of Study/Early Withdrawal CRF.

Days of Subject Diary Completion

Days of Subject Diary Completion is defined as the number of days from Day 1 to the date of last Subject Diary completion. For the purposes of this analysis, the date of last Subject Diary completion is defined as the last date in which the Subject Diary had at least one complete assessment of symptoms recorded.

Alleviation of Symptoms

A subject has Alleviation of Symptoms if all of the assessed symptoms of influenza assessed on his/her subject diary are either absent or are present at no more than mild severity level and at this status for a 21.5 hour period (24 hours less 10%).

Composite Symptom Score

The Composite Symptom Score is defined as the sum of the seven symptoms of influenza (cough, sore throat, stuffy nose, muscle aches, headache, feverishness, fatigue/tired) assessed on a given time point within the subject diary.

Baseline Composite Symptom Score

The Baseline Composite Symptom Score is defined as the sum of the symptoms of influenza recorded by the subject in the diary corresponding to the assessment of a subject's symptoms prior to the initiation of study drug.

Resolution of Fever

A subject has Resolution of Fever if he/she has a temperature < 37.4°C/99.4°F oral and no antipyretic medications have been taken for at least 12 hours. Resolution of Fever is based on information obtained from the individual subject diaries.

Ability to Perform Usual Activities

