The development of any post treatment genotypic changes in neuraminidase and hemagglutinin will be assessed by comparison of sequences from baseline and last positive post-treatment virus samples. These analyses will be presented overall and by age group and viral subtype.

The number and percentage of subjects experiencing influenza related complications will be summarized by age group and overall by complication MedDRA version 18.0 preferred term.

The number and percentage of subjects who are hospitalized due to any TEAE and due to any TEAE related to study drug after initiation of treatment will be summarized by age group and overall.

The number of doses of antipyretic medications, as recorded in the subject diary, taken throughout the study and by study day will be summarized by age group and overall.

The change in daily activities will be summarized each day by age group and overall. The ability to perform usual activities is defined as a subject rating of 10 (able to perform all usual activities fully) on the visual analog scale the subject uses to rate his or her current ability to perform usual activities compared with normal ability. The time to return to usual activities will be estimated for each age group and overall using the Kaplan-Meier method. Subjects who do not return to normal activities will be censored at the time of their last non-missing post-baseline assessment.

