6. CHANGES IN THE PLANNED ANALYSES

An analysis of the number of doses of antipyretic medications will be prepared.

There are no further changes anticipated to the protocol specified analyses. Should any more deviations occur, these changes will be fully described in the Clinical and Statistical Report.

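### Antipyretic doses are counted by calendar study day, so a partial Day 1 is set beside full later days and an early fall in use can be understated, hidden or reversed

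*SAP*

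**What the plan says.** Antipyretic use is one of the effectiveness endpoints in SAP 5.2.1. SAP 5.2.2 gives the analysis: "The number of doses of antipyretic medications, as recorded in the subject diary, taken throughout the study and by study day will be summarized". Results are shown for each age category and for all subjects together. The output is Table 14.2.8, in the ITTI population. SAP section 6 names this as the one change from the protocol's analyses: "An analysis of the number of doses of antipyretic medications will be prepared".

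SAP 3.3.8 sets the time unit: "Study Day = event date – date of Day 1 +1". The same section says "Day 1 is the day/time that study drug is initiated", but only the date enters the formula.

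On the diary, Protocol 10.1.2.2 opens with "The following procedures/evaluations will be performed post-dose on Day 1", and one of the listed procedures is "Train the subject/caregiver on the recording of the following in the subject diary". The items under that heading are temperature, usual activities with time lost from work, and symptoms; medication is not named. Protocol 9.9, which does cover the recording of symptomatic medication, says "Study staff will provide diary completion instructions to subjects during their first study visit" and gives no order relative to dosing. It also has subjects record the date and time of each such medication. Protocol 9.3 has the start and end times of the infusion recorded.

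**The concern.** A count per day can be compared across days only if each day is observed for the same length of time. Here Day 1 is cut short and the others are not, and the cut differs between subjects because it depends on when each was infused. The SAP offers no 24-hour windows, no hours-observed denominator and no footnote.

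The first days after a single infusion are where a reader will look for a change in antipyretic use. There is no control group in which the same Day 1 truncation would appear, so the time course within the treated subjects is what the table has to offer. A shortened Day 1 tilts that course upward: a true fall from Day 1 to Day 2 looks smaller than it was, disappears, or turns into an increase.

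**Working it through.** The documents give no figure to reproduce on this point. Infusion time, dose rate and rate of decline below are assumptions.

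**Observed share of Day 1.** With infusion at clock hour h and counting from infusion to midnight, f = (24 − h)/24. At an assumed constant 3 doses per 24 hours, the expected Day 1 count is 3f, against 3.0 on Day 2. The apparent rise is 1/f − 1.

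| Infusion | f | Day 1 count | Day 2 count | Apparent rise |
|---|---|---|---|---|
| 09:00 | 15/24 = 62.5% | 1.88 | 3.0 | 60% |
| 12:00 | 12/24 = 50% | 1.50 | 3.0 | 100% |
| 15:00 | 9/24 = 37.5% | 1.13 | 3.0 | 167% |
| 18:00 | 6/24 = 25% | 0.75 | 3.0 | 300% |

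**Doses only in waking hours.** If doses fall only between 07:00 and 23:00, the share is (23 − h)/16: 87.5%, 68.8%, 50% and 31.3%. The Day 1 counts become 2.6, 2.1, 1.5 and 0.9. The cut is smaller, and for a morning infusion it is modest.

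**Declining use, step model.** If true use on the second day is q times that on the first, the reported ratio is q/f. A rise appears only when q > f.

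**Declining use, exponential model.** If use falls smoothly from infusion with 24-hour ratio q, then k = −ln(q)/24, and the expected doses between a and b hours after infusion are proportional to I(a, b) = (e^(−ka) − e^(−kb))/k. The reported ratio is I(24 − h, 48 − h)/I(0, 24 − h), which equals q^f(1 − q)/(1 − q^f). For q = 0.5 and h = 12, q^f = 0.707 and the ratio is 0.707 × 0.5/0.293 = 1.21.

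| Reported Day 2/Day 1 ratio | 09:00 | 12:00 | 15:00 | 18:00 | True ratio |
|---|---|---|---|---|---|
| Step, q = 0.8 | 1.28 | 1.60 | 2.13 | 3.20 | 0.80 |
| Step, q = 0.5 | 0.80 | 1.00 | 1.33 | 2.00 | 0.50 |
| Exponential, q = 0.5 | 0.92 | 1.21 | 1.68 | 2.64 | 0.50 |
| Exponential, q = 0.25 | 0.54 | 0.75 | 1.10 | 1.81 | 0.25 |

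Every entry exceeds its true ratio. Some entries still show a fall, one is flat, and the rest show a rise.

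**If recording starts before infusion.** Suppose it starts at the clinic visit at hour v < h. The observed share is (24 − v)/24, larger than f but still below 1, so Day 1 remains partial. It now also mixes doses taken before and after treatment. SAP 3.3.8 classes medication taken before study drug as prior, and Protocol 10.2.1 foresees that some subjects will have taken an antipyretic shortly before the baseline temperature.

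**With 24-hour periods from infusion.** The reported ratio is I(24, 48)/I(0, 24) = q at any infusion time: 1.00 for constant use, 0.80 for a 20% fall, 0.50 for a halving.

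**The case against.** The strongest reply is that the table is only descriptive. The SAP tests no hypothesis, plans no formal Day 1 against Day 2 contrast, and has no control group, so a trend over the first two days could not be attributed to peramivir in any case. Time to resolution of fever draws on the diary temperatures and medication records directly and does not depend on this table. All of this stands and limits the importance of the point. It does not make the daily counts comparable.

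Four stronger readings are tempting, and the documents do not support them.

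- **The diary starts only after dosing.** A reader might infer this from Protocol 10.1.2.2, but the training items there omit medication, and Protocol 9.9 places the instructions at the first visit without saying when. Other text points to diary content before dosing: SAP 3.3.8 takes the baseline symptom score from a diary entry about symptoms before study drug, and Protocol 10.1 lists a Screening symptom assessment among the diary items. Neither document states when the medication record begins.
- **A false rise must appear on Day 2.** It follows for constant use, but with declining use it depends on infusion time and speed of decline, as the second table shows.
- **The age-group columns are biased against each other.** That requires infusion times to differ by age group, and nothing in the documents says they do.
- **The study total should be divided by diary days.** Protocol 10.2.2 lets subjects stop recording symptoms after 48 hours at absent or mild, and SAP 3.3.8 dates the last diary completion by a symptom entry. That denominator would depend on the outcome: subjects who recover quickly would get short denominators and inflated rates.

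**Conclusion.** The point holds as a minor one. Under the stated rule, Day 1 is a partial window that varies by subject, while later days cover 24 hours, and the early time course of a listed effectiveness endpoint is tilted upward. For infusion between 09:00 and 18:00, 62.5% to 25% of Day 1 is observed on a 24-hour basis, or 87.5% to 31.3% if doses are confined to 07:00 to 23:00. A true halving would be reported as a Day 2/Day 1 ratio of 0.80 to 2.00 (step) or 0.92 to 2.64 (exponential).

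These sizes rest on assumed infusion times and patterns of use, and on counting from infusion; recording from an earlier clinic visit would shrink the cut but add pre-dose use. The direction assumes that Day 1 recording begins during that day, which fits the protocol's expectation that most subjects are screened and dosed on the same day. The effect stays within a descriptive, non-primary table. No error rate, sample size or safety conclusion changes.

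**What to change.** In SAP 5.2.2 and Table 14.2.8, replace the count by study day with consecutive 24-hour periods from the start of infusion (0–24 h, >24–48 h, and so on). Count only doses taken after the infusion starts. State in the SAP when the medication record begins, so that it is clear whether the hours between infusion and leaving the clinic are covered.

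The cost is a change of SAP wording and a short derivation from dose and infusion times already collected. There are two small downsides:

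- **Missing dose times.** A dose with a date but no time cannot be placed without a rule, because each calendar date straddles two periods. The imputation in SAP 3.3.4 covers diary completion times, not dose times. Add a rule and report how many doses it affects.
- **Partial last period.** A subject's last period may be incomplete and needs a footnote.

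If the calendar layout is kept, the least that is needed is a footnote marking Day 1 as a partial day, together with the statement of when medication recording starts.

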### 10.2.3. Assessment of ability to perform usual daily activities

If possible, subjects/caregivers will be asked to provide a daily assessment of the subject's ability to perform usual daily activities using a 0 to 10 visual analogue scale, where 0 = Unable to perform usual activities at all, and 10 = Able to perform usual activities fully. The subject will also assess his/her time lost from work, if applicable. The subject/care giver will be asked to record these assessments in the subject diary once daily from Baseline through Day 13 and prior to the subject's clinic visit on Day 14.

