The ability to perform usual activities is defined as a subject rating of 10 (able to perform all usual activities fully) on the visual analog scale the subject uses to rate his or her current ability to perform usual activities compared with normal ability.

Time to Event

Time to a given event is defined as the number of hours (days) from initiation of earliest study treatment until the event occurs. The unit of measurement will vary based upon the endpoint and its respective schedule of assessment.

Time to Alleviation of Symptoms

Time to Alleviation of Symptoms is the number of hours from initiation of study drug to start of the 21.5 hour period (24 hours less 10%) where all symptoms of influenza are recorded as none or mild.

Change from Baseline

Change from baseline for a given endpoint is defined as the Study Day X value minus the Baseline Value.

Adverse Event (AE)

According to the protocol, an AE is any untoward medical occurrence in a clinical study subject. No causal relationship with the study drug or with the clinical study itself is implied. An AE may be an unfavorable and unintended sign, symptom, syndrome, or illness that develops or worsens during the clinical study. Clinically relevant abnormal results of diagnostic procedures including abnormal laboratory findings (eg, requiring unscheduled diagnostic procedures or treatment measures, or resulting in withdrawal from the study) are considered to be AEs.

AEs may be designated as “nonserious” or “serious” (see Protocol Section 11.1.1.1). Surgical procedures are not AEs but may constitute therapeutic measures for conditions that require surgery. The condition for which the surgery is required is an AE if it occurs or is detected during the study period. Planned surgical measures permitted by the clinical study protocol and the condition(s) leading to these measures are not AEs if the condition(s) was (were) known before the start of study treatment. In the latter case the condition should be reported as medical history.

Assessment of symptoms of influenza will be documented in a Subject Diary and analyzed as a measure of effectiveness of the study treatment. These symptoms will not be reported as AEs unless the symptom(s) worsen to the extent that the outcome fulfills the definition of a serious adverse event (SAE), which then must be recorded as such (see Protocol Section 11.1.1.2).

All AEs will be recorded on the ADVERSE EVENTS CRF.

Treatment-emergent Adverse Events (TEAEs)

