5.2.2. Effectiveness Analyses

A subject's oral temperature taken by subjects and recorded in the diary by subjects/caregivers will be summarized by age group and overall by study visit. A subject has Resolution of Fever if he/she has an oral temperature $< 37.4^{\circ}\text{C}/99.4^{\circ}\text{F}$ oral and no antipyretic medications have been taken for at least 12 hours. The time to resolution of fever will be estimated for each age group and overall using the Kaplan-Meier method with temperature and symptom relief medication information obtained from the subject diary data. Subjects who do not have resolution of fever will be censored at the time of their last non-missing post-baseline temperature assessment.

Alleviation of symptoms will be determined by assessment of symptoms as reported on each Subject Diary. The time to alleviation of symptoms, defined as the time from initiation of study drug until the start of the 21.5 hour period (24 hours less 10%) where all symptoms of influenza are recorded as none or mild, will be estimated overall and for each age group using the Kaplan-Meier method. Subjects who do not experience alleviation of symptoms will be censored at the date of their last non-missing post-baseline assessment.

Change from baseline in \log_{10} TCID₅₀/mL through Day 3, Day 7, and Day 14 will be presented by age group and overall for subjects with positive viral titers at baseline (\log_{10} TCID₅₀/mL > 0.5). A box plot and a histogram of the TCID₅₀/mL values will be presented by visit and age group. In addition, the median change from baseline in TCID₅₀/mL will be presented by visit and age group.

The number and percent of subjects with positive viral titers at baseline (\log_{10} TCID₅₀/mL > 0.5) that shed virus at each visit will be presented by age group and overall.

The RT-PCR results at each visit will be presented by age group and overall for subjects with positive RT-PCR results at baseline.

Change from baseline to last positive value of influenza virus susceptibility to neuraminidase inhibitors will be assessed using virology laboratory tests. Virology laboratory tests will include phenotypic characterizations of influenza virus recovered (hemagglutinin and neuraminidase) and viral susceptibility to zanamivir, oseltamivir, and peramivir, as well as genotyping of virus isolates. These analyses will be presented overall and by age group and viral subtype.

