Figure 14.2.3.4	Median (with IQR) Change from Baseline Viral Titers (TCID ₅₀ /mL) by Study Visit: Subjects with Positive Baseline Titers: Intent-to-Treat Infected Population
Table 14.2.4.1	Summary of Viral Shedding by Study Visit; Subjects with Positive Baseline Titers: Intent-to-Treat Infected Population
Table 14.2.4.1.X	Summary of Viral Shedding by Study Visit: Subjects with Positive Baseline Titers: Viral Subtype: Intent-to-Treat Infected Population
Table 14.2.5.1	Summary of RT-PCR Result by Study Visit: Subjects with Positive Baseline RT-PCR: Intent-to-Treat Infected Population
Table 14.2.5.1.X	Summary of RT-PCR Result by Study Visit: Subjects with Positive Baseline RT-PCR: Viral Subtype: Intent-to-Treat Infected Population

Output Number	Output Title
Table 14.2.6	Change of Influenza Virus Susceptibility to Neuraminidase Inhibitors: Intent-to-Treat Infected Population
Table 14.2.7	Summary of Influenza-Related Complications and Hospitalizations: Intent-to-Treat Infected Population
Table 14.2.8	Number of Doses of Antipyretic Medications: Intent-to-Treat Infected Population
Table 14.2.9.1	Summary of Subject-Rated Assessment of Ability to Perform Daily Activities: Intent-to-Treat Infected Population
Table 14.2.9.2	Time to Return to Usual Activities: Intent-to-Treat Infected Population
Table 14.3.1.1	Overall Summary of Treatment-Emergent Adverse Events: Safety Population
Table 14.3.1.2	Treatment-Emergent Adverse Events by System Organ Classification, Preferred Term and Greatest Severity: Safety Population
Table 14.3.1.3	Treatment-Emergent Adverse Events by System Organ Classification and Preferred Term: Safety Population
Table 14.3.1.4	Treatment-Emergent Adverse Events Possibly, Probably, or Definitely Related to Study Drug by System Organ Classification and Preferred Term: Safety Population
Table 14.3.1.5	Treatment-Emergent Serious Adverse Events by System Organ Classification and Preferred Term: Safety Population
Table 14.3.1.6	Treatment-Emergent Adverse Events Leading to the Discontinuation of Study by System Organ Classification and Preferred Term: Safety Population
Table 14.3.1.7	Treatment-Emergent Adverse Events Leading to the Discontinuation of Study Drug by System Organ Classification and Preferred Term: Safety Population
Table 14.3.1.8	Treatment-Emergent Adverse Events Occurring in $\geq 10\%$ of Subjects by Preferred Term: Safety Population

Output Number	Output Title

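### Time to return to usual activities does not require a baseline rating below 10, so subjects who were never limited could enter as immediate events and lower the median

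*SAP*

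**What the plan says.** SAP 5.2.2 names the estimator: "The time to return to usual activities will be estimated for each age group and overall using the Kaplan-Meier method". The same section sets the event: "The ability to perform usual activities is defined as a subject rating of 10 (able to perform all usual activities fully". SAP 3.3.8 gives the clock: "Time to a given event is defined as the number of hours (days) from initiation of earliest study treatment until the event occurs". The only censoring rule in SAP 5.2.2 for this endpoint is: "Subjects who do not return to normal activities will be censored at the time of their last non-missing post-baseline assessment". Table 14.2.9.2 in SAP section 9 is titled "Time to Return to Usual Activities: Intent-to-Treat Infected Population", with no restriction on the baseline rating.

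The rating is meant to exist before treatment. Protocol Table 1 schedules it at Baseline, and Protocol 10.2.3 asks for it "once daily from Baseline through Day 13", with a last rating before the Day 14 visit.

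Elsewhere SAP 5.2.2 does restrict an analysis to subjects who can show the change of interest. For example: "The RT-PCR results at each visit will be presented by age group and overall for subjects with positive RT-PCR results at baseline". The titer-change and shedding summaries are likewise limited to subjects with a positive titer at baseline.

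**The concern.** A return to usual activities presupposes that the subject was limited to begin with. The plan does not impose that condition. A subject who rates 10 before dosing and stays at 10 meets the event definition at the first rating used. That subject is not covered by the censoring rule and is not removed by the population definition. A programmer following the text would record an event at or near time zero, so someone never at risk of the event would be analysed as one of the fastest to recover.

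Such subjects can be enrolled. The inclusion criteria in Protocol 8.1 set conditions on test result, symptoms, onset and risk group, but none on activity. Under SAP 5.2.2 subjects rate themselves against their own normal ability, so a person whose usual activity is modest, such as a nursing-home resident, could rate 10 while ill.

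The design gives the artefact nowhere to cancel. This is a single-arm study, and the absolute median is what a reader will take away.

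**Working it through.** The plan states no expected median or sample-size formula for this endpoint, so there is no figure of its own to reproduce. The calculation below only shows scale.

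**Inputs**
- Share p of ITTI subjects already at 10 and staying there: not in the documents, so assumed at 0%, 2%, 5% and 10%.
- Median m among limited subjects: assumed at 7 and 11 days. Protocol 5.1 gives 7 to 11 days as background for the delay in returning to normal health and activities. It is not a design assumption.
- Shape of the time distribution F among limited subjects: Weibull, shape k from 1 (exponential) to 2, assumed.

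**Formula.** If the share p is counted as an event at the start, the reported median t solves p + (1 − p)F(t) = 0.5. Hence F(t) = (0.5 − p)/(1 − p), and t = m × [−ln(1 − F)/ln 2]^(1/k).

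**Example, p = 5%, m = 7.** F = 0.45/0.95 = 0.4737, and −ln(0.5263)/0.6931 = 0.926. With k = 1, t = 7 × 0.926 = 6.48 days. With k = 2, t = 7 × √0.926 = 7 × 0.962 = 6.73 days.

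| p | F(t) | Fraction of m (k = 1 to 2) | m = 7 days | m = 11 days |
|---|---|---|---|---|
| 0% | 0.5000 | 1 | 7.0 | 11.0 |
| 2% | 0.4898 | 0.971 to 0.985 | 6.80 to 6.89 | 10.68 to 10.83 |
| 5% | 0.4737 | 0.926 to 0.962 | 6.48 to 6.73 | 10.19 to 10.58 |
| 10% | 0.4444 | 0.848 to 0.921 | 5.94 to 6.45 | 9.33 to 10.13 |

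**Does it matter where the event is placed?** The SAP does not say whether the baseline rating itself can be the event or only a later one. A simulation compared the options with 120 subjects, daily ratings, exponential times with a 7-day median, censoring at Day 13, p = 10% and 500 runs. The mean Kaplan-Meier median was 6.43 days with the event at time zero, 6.42 days with it at the first post-baseline rating, and 7.59 days with these subjects excluded. (The simulated values sit above the closed form because times are rounded up to whole days.) The downward shift is therefore practically the same under either reading that keeps these subjects as events. It disappears if they are excluded or if p is zero.

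**The case against.** A reader might infer that the SAP has a rule counting subjects at 10 as returned at the start. It does not. No sentence counts them, excludes them or censors them, and the endpoint's own name, return or resumption, could be read as leaving them out. The supportable statement is that handling is unspecified and that literal application would count them.

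A reader might also infer that the test-positive route admits one symptom of any severity, so that fully active subjects are to be expected. The documents do not settle this. Protocol 8.1 criterion 2a refers to the symptoms listed in 2b, which are of at least moderate severity. Protocol 10.1.1 adds, after both routes, that a subject must have a respiratory and a constitutional symptom of at least moderate severity. Protocol 10.2.2 describes moderate as very uncomfortable. If that sentence applies to everyone, few subjects should rate exactly 10. It still concerns symptoms rather than activity, so it makes the case less likely without excluding it.

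On size, no share has a source in the documents. At 2% and 5% the shift from 7 days is about 0.1 to 0.2 and 0.3 to 0.5 day, less than the one-day interval between ratings. The exponential shape gives the largest shift of those tried. A distortion between age groups is conceivable if baseline limitation differs by age, but no data in the documents support it.

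On consequence, the primary endpoint is safety and no hypothesis is tested. This endpoint appears in the protocol synopsis and the SAP but not in Protocol 7.1.2 or 13.8.2. Table 14.2.9.1 and Listing 16.2.6.4 would make ratings of 10 at baseline visible. That helps a careful reader but does not correct the median in Table 14.2.9.2.

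Finally, a pre-dose rating is less certain than Table 1 suggests. Protocol 10.1.2.1 omits it from the baseline procedures, 10.1.2.2 places instruction on the scale after dosing, and 10.2.3 asks for it only if possible. This objection stands, and the fix has to deal with it.

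**Conclusion.** The gap is real but modest. The plan analyses a return in the whole ITTI population without requiring that the subject was below 10 at the start. If subjects already at 10 are kept as events, the median is biased downward. On an assumed 7-day median and Weibull shape 1 to 2, the shift is about 0.1 to 0.2 day at a 2% share, 0.3 to 0.5 day at 5% and 0.6 to 1.1 days at 10%. It is zero if no such subject is enrolled. The direction follows from the definitions once these subjects are counted. The size rests entirely on the assumed share, median and shape. Because the endpoint is secondary and descriptive, no error rate, power or sample size is touched. The change is worth making because it is cheap, matches what the SAP already does for the virology summaries, and removes a decision that would otherwise be left to programming.

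**What to change.** In SAP 5.2.2, and in the title or a footnote of Table 14.2.9.2:

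- Limit the main Kaplan-Meier analysis of return to usual activities to ITTI subjects with a baseline rating below 10.
- Report, by age group and overall, the number already at 10 and the number with no pre-dose rating.
- State how a missing baseline rating is handled. This should cover a Day 1 diary rating with no recorded time, because SAP 3.3.4 sets untimed daily entries to 23:59 and so places them after a dose given earlier that day.
- Show the full ITTI result as a sensitivity analysis, saying whether the baseline rating itself can be the event.

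The cost is a few sentences, a footnote and one additional run of the same analysis, with no new data collection. The analysis set becomes slightly smaller, and it loses any subject at 10 at baseline who later worsens and then recovers. The sensitivity analysis keeps that subject in view.
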